10.4.4 Supportive and sensitivity analyses

The following analyses of PFS will be performed in the *PIK3CA* mutant cohort to support the primary PFS analysis, where the primary endpoint is statistically significant.

A sensitivity analysis to support the primary PFS analysis will be conducted where patient's PFS times are censored at the onset of new anticancer therapy.

Subgroup analyses of PFS may be performed in the *PIK3CA* mutant cohort (if the primary endpoint is statistically significant) based on each level of the stratification factors and other prognostic baseline demographic or disease characteristic factors listed below:

- Age
- Race
- ECOG performance status at baseline
- Measurable vs. non-measurable lesions at baseline
- Previous treatment with endocrine therapy for metastatic disease

Additional baseline disease characteristic factors that are deemed relevant may be specified in the SAP. The analyses for the subgroups will include hazard ratios (together with associated two-sided 95% confidence intervals) from un-stratified Cox proportional hazards models.

In addition, the analysis of PFS using stratified Cox proportional hazards model may be repeated using the PPS in the cohort where the primary endpoint is statistically significant.

PFS events will be described according to the type of events (death, documented progression) by treatment arm in the FAS. Censoring reasons will be described by treatment arm. A sensitivity analysis to support the primary PFS analysis will be conducted where patient's PFS times are censored at the onset of new anticancer therapy.

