3.8.1.1 Primary analysis

The primary analysis of PFS will be based on the local radiological assessments (Source 1 in [Table 3-2](#)) up until the cut-off date defined in [Section 2.2](#). The analysis will be performed on the FAS and will use the default censoring and event date options from [Table 3-3](#), with the

exception of the rules for new antineoplastic therapy given, i.e. event/censoring rules will be based on options A(1), B(1), C1(1), C2(1), D(1), E(1), and F(1). In particular, PFS will be censored at the last adequate tumor assessment if a patient didn't have an event or the event occurred after two or more missing tumor assessments (see [Section 2.4.5](#)). In the primary analysis in this study PFS will not be censored if a new antineoplastic therapy is started; instead, an ITT approach will be used and this new antineoplastic therapy will be ignored for the purposes of PFS derivation (and tumor assessments will continue), i.e. option F(1) in [Table 3-3](#) will be used. A sensitivity analysis will be performed censoring PFS at the last adequate tumor assessment prior to start of new antineoplastic therapy, i.e. using option F(2). Discontinuation of study treatment (for any reason) will not be considered as a reason for censoring.

Table 3-3 Options for event dates used in PFS

Situation		Options for end-date (progression or censoring) ¹ (1) = default unless specified differently in the protocol or RAP	Outcome
A	No baseline assessment	(1) Date of randomization/start of treatment ³	Censored
B	Progression at or before next scheduled assessment	(1) Date of progression (2) Date of next scheduled assessment ²	Progressed Progressed
C1	Progression or death after exactly one missing assessment	(1) Date of progression (or death) (2) Date of next scheduled assessment ²	Progressed Progressed
C2	Progression or death after two or more missing assessments	(1) Date of last adequate assessment ² (2) Date of next scheduled assessment ² (3) Date of progression (or death)	Censored Progressed Progressed
D	No progression	(1) Date of last adequate assessment	Censored
E	Treatment discontinuation due to 'Disease progression' without documented progression, i.e. clinical progression based on investigator claim	(1) Ignore clinical progression and follow situations above (2) Date of discontinuation (visit date at which clinical progression was determined)	As per above situations Progressed

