F	New anticancer therapy given	(1) Ignore the new anticancer therapy and follow situations above (ITT approach) (2) Date of last adequate assessment prior to new anticancer therapy (3) Date of secondary anti-cancer therapy (4) Date of secondary anti-cancer therapy	As per above situations Censored Censored Event
G	Deaths due to reason other than deterioration of 'Study indication'	(1) Date of last adequate assessment	Censored (only TTP and [REDACTED])

¹.=Definitions can be found in Protocol Appendix 3 Section 14.3.25².=After the last adequate tumor assessment. "Date of next scheduled assessment" is defined in Protocol Appendix 3 Section 14.3.25.³.=The rare exception to this is if the patient dies no later than the time of the second scheduled assessment as defined in the protocol in which case this is a PFS event at the date of death

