3.8.1.5 Sensitivity analyses of the primary endpoint

Sensitivity analyses are performed only if the analysis of primary endpoint in the PIK3CA mutant cohort shows statistically significant results. Subgroup analyses to explore the intrinsic consistency of any treatment effect found overall are specified in [Section 3.13.2](#).

Per protocol Population

The PPS will be used to perform sensitivity analysis for the primary efficacy endpoint (i.e. PFS) if the primary endpoint is statistically significant.

Different Censoring Mechanisms

Depending on the statistical significance of the primary efficacy endpoint, the following sensitivity analyses will be performed to address the impact of tumor assessment features and censoring rules on primary analyses. The primary efficacy analyses in each cohort; i.e. the stratified log-rank test, Kaplan-Meier estimates, estimate of the median PFS along with 95% confidence interval, and hazard ratio obtained using the Cox proportional hazards model, will be repeated (as appropriate) based on the data obtained:

1. If more than 10% patients have two or more consecutive missing assessments prior to PFS event, primary PFS analyses will be repeated using investigator/local assessment (Source 1 in [Table 3-2](#)) on the FAS and taking the event whenever it occurs - even after two or more missing tumor assessments. The following options from [Table 3-3](#) will be used: A(1), B(1), C1(1), C2(3), D(1), E(1) and F(1). In the summary table, this approach is referred as 'Actual event PFS analysis'
2. If more than 10% patients have two or more consecutive missing assessments prior to PFS event, primary PFS analyses will be repeated using investigator/local assessment (Source 1 in [Table 3-2](#)) on the FAS and backdating events occurring after missing tumor assessments. The following options from [Table 3-3](#) will be used: A(1), B(1), C1(2), C2(2), D(1), E(1), and F(1). In the summary tables, this approach is referred as 'Backdating PFS analysis' where, the date of next scheduled assessment is defined as the date of the last adequate tumor assessment plus the protocol specified time interval for assessments.
3. Using investigator/local assessment (Source 1 in [Table 3-2](#)) on the FAS and censoring all PFS events that occur after the start of new anti-neoplastic therapy to the time of last adequate tumor assessment done prior to the therapy start date.

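### SAP 3.8.1.5 item 3 words the new-therapy sensitivity analysis of PFS differently from option F(2) and Protocol 10.4.4; programmed as written, it would favour whichever arm switches therapy more before progression

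*SAP*

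**What the plan says.** The primary PFS analysis follows option F(1): new therapy is disregarded and scans go on ("this new antineoplastic therapy will be ignored for the purposes of PFS derivation (and tumor assessments will continue"). One sensitivity analysis is then planned for new therapy, and it is described in three places.

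- **SAP 3.8.1.1** gives the date and the option code ("censoring PFS at the last adequate tumor assessment prior to start of new antineoplastic therapy, i.e. using option F(2"). In Table 3-3, situation F is that new anticancer therapy was given, and F(2) assigns "Date of last adequate assessment prior to new anticancer therapy" with outcome censored. No later event is required.
- **SAP 3.8.1.5, Different Censoring Mechanisms, item 3** describes it as "censoring all PFS events that occur after the start of new anti-neoplastic therapy to the time of last adequate tumor assessment" made before the start of therapy. Items 1 and 2 each list a full string of options from A to F. Item 3 lists none.
- **Protocol 10.4.4** describes an analysis in which "PFS times are censored at the onset of new anticancer therapy". That is closest to option F(3), which has a different date.

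SAP 3.8.1.5 also limits when the analysis is run: "Sensitivity analyses are performed only if the analysis of primary endpoint in the PIK3CA mutant cohort shows statistically significant results".

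**The concern.** Item 3 and F(2) use the same censoring date but cover different patients. F(2) covers everyone who starts new therapy. Item 3, read literally, covers only those who go on to have a PFS event.

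Take two patients who both start new therapy at month 3. With 8-weekly scans the last scan before it is at week 8, or 8 × 7 / 30.4375 = 1.8 months. One progresses at month 9; the other is event-free at month 9. Under F(2) both are censored at 1.8 months. Under item 3 as written, the first is censored at 1.8 months and the second keeps all 9 months. Whether a patient's later follow-up counts then depends on how that follow-up turned out. This lowers the apparent hazard in any arm with switchers, and lowers it more in the arm with more of them.

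The purpose of this analysis is to show whether the PFS result depends on how new therapy is handled. A rule that responds to switching imbalance in this way could reassure or alarm for the wrong reason.

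**Working it through.** **Inputs from the SAP.** Sections 3.12.1 and 3.14: 243 PFS events, HR 0.6, one-sided 2.0%, control median 7.0 months, 340 patients 1:1, accrual 5, 14 and 24 per month, 10% lost; boundaries Z = 1.489 (futility, 97 events), 3.719 (185 events) and 2.054 (final). Section 2.4.3: scans every 8 weeks for 18 months, then every 12 weeks, ±7 days. **Assumed:** the share of patients starting new therapy before progression, because the documents give none.

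**Step 1: the plan's own figure.** A fixed design gives Φ(√243 × |ln 0.6| / 2 − 2.054) = Φ(3.981 − 2.054) = 97.3%, not the stated 83.80%. With three looks, and the cohort stopped whenever Z at the first look is below 1.489, simulation gives 84.0%. The design inputs are therefore understood.

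**Step 2: three rules on that design.** PFS is exponential with control hazard λ = ln 2 / 7.0 = 0.099 per month. For a share p switching before progression, the switching hazard is μ = λp / (1 − p), using each arm's own λ; for control at p = 5%, 0.099 × 0.05 / 0.95 = 0.0052 per month. Data are cut at 243 documented events, and the hazard ratio comes from an unstratified Cox model, with 1,500 trials per row. The Monte Carlo standard error of a mean log HR is about (2/√243)/√1,500 = 0.128/38.7 = 0.0033. Switching here is unrelated to prognosis.

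| True HR | Switching, control / alpelisib | F(1) | Item 3 as written | F(2) | Item 3 relative to F(1) |
|---|---|---|---|---|---|
| 1.0 | 10% / 10% | 0.995 | 0.996 | 0.996 | +0.1% |
| 1.0 | 5% / 15% | 1.003 | 0.970 | 1.015 | −3.3% |
| 1.0 | 15% / 5% | 1.006 | 1.041 | 0.995 | +3.5% |
| 1.0 | 10% / 30% | 1.003 | 0.918 | 1.033 | −8.5% |
| 1.0 | 30% / 10% | 1.002 | 1.093 | 0.973 | +9.1% |
| 0.6 | 10% / 10% | 0.601 | 0.603 | 0.598 | +0.3% |
| 0.6 | 5% / 15% | 0.600 | 0.583 | 0.605 | −2.8% |
| 0.6 | 15% / 5% | 0.602 | 0.626 | 0.595 | +4.0% |
| 0.6 | 10% / 30% | 0.602 | 0.557 | 0.610 | −7.5% |
| 0.6 | 30% / 10% | 0.604 | 0.667 | 0.584 | +10.4% |

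Few patients drive this. At true HR 1.0, switchers still event-free at the cut-off are 3.6% of the cohort in the 10-point rows (0.036 × 340 = 12 patients) and 7.4% in the 20-point rows (25 patients).

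**Step 3: intermediate gaps.** A separate simulation with fixed 56-day scans and a 32-month cut-off, at true HR 0.6, gives 0.62 under both the primary rule and F(2). Item 3 as written gives 0.60 (5%/12%), 0.58 (5%/19%) and 0.56 (8%/27%), which are shifts of −3%, −6% and −10%. At true HR 1.0 it gives 0.96 (5%/16%) and 0.94 (8%/22%), against 1.00-1.01 under F(2).

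**Step 4: prognosis-related switching.** If the hazard rises 1.5-fold after a switch, then at true HR 1.0 and 10%/30% the three rules give 1.062, 0.958 and 1.034. At 30%/10% they give 0.946, 1.050 and 0.971. Item 3 still moves towards the arm that switches more, relative to both F(1) and F(2).

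Simplifications: progression events only, no missed scans.

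**The case against.** The strongest reply is that the rule is already settled. SAP 3.8.1.1 announces this analysis and names F(2); item 3 uses F(2)'s date; and Protocol Appendix 3 (14.3.28, situation F) recommends the same analysis with no restriction to patients who later have events. On that view item 3 is an incomplete restatement, and a programmer has an option code to follow. Much of this stands. Item 3 never says that event-free switchers keep their later follow-up; that follows only from its silence. A reader might infer that the SAP prescribes an event-only rule, and the documents do not support that.

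What remains is that the section specifying the sensitivity analyses is the one with the narrower wording and no option codes. Elsewhere the SAP is explicit when it means all patients: the ECOG rule (3.8.2.8) censors every patient who receives further therapy before worsening.

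A reader might also infer that the analysis is tilted towards alpelisib because of its toxicity. The documents do not support that either. Stopping alpelisib is not starting new therapy: Protocol 6.1.2 lets patients stay on fulvestrant alone. For best response, SAP 2.4.3 does not count continued fulvestrant monotherapy as new therapy, although no such statement is made for PFS. Control patients could switch more, for instance after clinical progression without RECIST evidence, which is not an event under E(1).

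F(2) is not exactly neutral: at true HR 1.0 it ranges from 0.973 to 1.033 in the table. Censoring at onset gave the same HR as F(2) in the fixed-scan simulation, so the Protocol difference is one of wording, with no numerical effect shown.

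**Conclusion.** The inconsistency between item 3, option F(2) and Protocol 10.4.4 is certain from the text. The bias is conditional on two things: that item 3 is programmed literally, and that the arms differ in how often patients start new therapy before progression. Given both, the hazard ratio shifts by about 3-7% for a gap of 10-15 points and up to about 10% for 20 points, measured against F(1). The shift favours alpelisib if alpelisib patients switch more, goes against it if control patients do, and is negligible at equal rates. All switching shares are assumptions.

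The consequence is limited. The primary analysis is untouched, no alpha is attached, and the analysis runs only after a significant primary result. The rows at true HR 1.0 show the direction of bias; they are not an error rate for any claim. This does not put the primary PFS result in doubt. It is worth correcting because a robustness check should follow one stated rule, and item 3's wording can give a misleading answer.

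**What to change.** In SAP 3.8.1.5 item 3, list the options as items 1 and 2 do: A(1), B(1), C1(1), C2(1), D(1), E(1), F(2). State that every patient who starts new anti-neoplastic therapy before a PFS event is censored at the last adequate tumor assessment before the therapy start, whether or not an event follows. Add a note that this replaces the onset wording of Protocol 10.4.4.

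The cost is one sentence and a note, with no new data. Since Protocol Amendment 5 records that the primary endpoint was met, the sponsor should also state which rule was programmed, and rerun this one analysis if it was the literal one.

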10.4.3 Handling of missing values/censoring/discontinuations

PFS times will be censored if no PFS event is observed before the cut-off date. The censoring date will be the date of last adequate tumor assessment before the cut-off date. If a PFS event is observed after two or more missing or non-adequate tumor assessments, then PFS will be censored at the last adequate tumor assessment. If a PFS event is observed after a single missing or non-adequate tumor assessment, the actual date of event will be used (see RECIST 1.1. [Appendix 3](#)). It is not intended to censor patients for new anticancer therapy prior to documented disease progression in the primary analysis.

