14.3.26 Definition of start and end dates for time to event variables

Assessment date

For each assessment (i.e. evaluation number), the **assessment date** is calculated as the latest of all measurement dates (e.g. X-ray, CT-scan) if the overall lesion response at that assessment is CR/PR/SD/UNK. Otherwise - if overall lesion response is progression - the assessment date is calculated as the earliest date of all measurement dates at that evaluation number.

In the calculation of the assessment date for time to event variables, any unscheduled assessment should be treated similarly to other evaluations.

Start dates

For all “time to event” variables, other than [REDACTED], the randomization/ date of treatment start will be used as the start date.

For the calculation of [REDACTED] the following start date should be used:

End dates

The end dates which are used to calculate ‘time to event’ variables are defined as follows:

- Date of death (during treatment as recorded on the treatment completion page or during follow-up as recorded on the study evaluation completion page or the survival follow-up page).
- Date of progression is the first assessment date at which the overall lesion response was recorded as progressive disease.
- Date of last adequate tumor assessment is the date the last tumor assessment with overall lesion response of CR, PR or SD which was made before an event or a censoring reason occurred. In this case the last tumor evaluation date at that assessment is used. If no post-baseline assessments are available (before an event or a censoring reason occurred) the date of randomization/start of treatment is used.
- Date of next scheduled assessment is the date of the last adequate tumor assessment plus the protocol specified time interval for assessments. This date may be used if back-dating is considered when the event occurred beyond the acceptable time window for the next tumor assessment as per protocol (see [Section 14.3.27](#)).

Example (if protocol defined schedule of assessments is 3 months): tumor assessments at baseline - 3 months - 6 months - missing - missing - PD. Date of next scheduled assessment would then correspond to 9 months.

- Date of discontinuation is the date of the end of treatment visit.

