2.4.6 No baseline tumor assessments

As specified in Table 14-9 in Appendix 3 of the study protocol, since the timing of disease progression cannot be determined for patients with missing baseline tumor assessment, these patients are censored in the PFS analysis at the date of randomization. This rule, however, only applies to the ‘progressive disease’ component of the PFS assessment.

Patients without any baseline tumor assessment who die within D2 time interval ([Section 2.4.5](#)) from date of randomization will be counted as having an event in the analysis of PFS at the date of death. All deaths will be counted in the overall survival analysis regardless of presence or absence of the baseline tumor assessment.

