3.8.1 Primary efficacy

The primary objective of the study is to determine whether treatment with alpelisib in combination with fulvestrant prolongs PFS compared to treatment with placebo in combination with fulvestrant in men and postmenopausal women with HR+, HER2-negative advanced breast cancer which progressed on or after AI treatment for patients with PIK3CA mutant status as measured in tissue.

PFS based on local radiology assessment is the primary efficacy variable in this study. PFS is defined as the time from the date of randomization to the date of the first documented disease progression or death due to any cause. If a patient has not progressed or died at the analysis cutoff date, PFS will be censored at the time of the last adequate tumor assessment before the cut-off date. Definitions and further details on PFS can be found in Appendix 3 of the study protocol.

Discontinuation due to disease progression (collected on the 'End of Treatment Disposition' and 'End Post Trt Phase Disposition' eCRF) without supporting objective evidence (as defined in [Section 2.4.2](#)) satisfying progression criteria per RECIST will not be considered disease progression for PFS derivation.

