4. If there are any COVID-19 related deaths, an additional sensitivity analysis will be performed to address the potential impact of the COVID-19 pandemic, using investigator/local assessment (Source 1 in [Table 3-2](#)) on the FAS and censoring all death events related to COVID-19 at the time of the event.

Unstratified Analysis

As a sensitivity analysis to assess the impact of stratification, the two treatment groups will be compared using the unstratified log-rank test. The HR together with the associated 95% confidence interval obtained using the unstratified Cox regression model will also be presented.

Baseline Demographic and Disease Characteristic factors

If the primary endpoint is statistically significant, a multivariate stratified Cox regression model for PFS will be fitted to evaluate additionally the effect of other baseline demographic or disease characteristics on the estimated hazard ratio. This model will include the following key

prognostic factors: ECOG performance status (0 vs. 1), bone lesions only at baseline (yes or no), number of prior lines of therapy in any setting (1st line vs 2nd line) and region (see [Section 3.13.2](#) for definitions).

All covariates will be included in the model regardless of their observed significance (p-value for given covariate). Forest plots for these factors will be provided, please see [Section 3.13.2](#).

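### The COVID-19 sensitivity analysis of PFS censors at the date of death, where the plan's other PFS rules for patients with a usable scan go back to the last adequate tumor assessment

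*SAP*

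**What the plan says.** Item 4 of the censoring-based sensitivity analyses in SAP 3.8.1.5 applies if any COVID-19 death occurs. It uses investigator assessments on the FAS, "censoring all death events related to COVID-19 at the time of the event". Items 1 and 2 of the same list name their Table 3-3 options; item 4 names none. SAP Amendment 5 (28 May 2020) added it, for the final OS cut-off.

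Elsewhere, PFS censoring goes back to the last adequate tumor assessment (LATA):

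- SAP 3.8.1, no progression or death by the cut-off: "PFS will be censored at the time of the last adequate tumor assessment before the cut-off date".
- SAP 3.8.1.1, options D(1) and C2(1): "PFS will be censored at the last adequate tumor assessment if a patient didn't have an event", and likewise if the event follows two or more missing assessments.
- SAP 3.8.1.5, item 3 (option F(2)), new therapy: "to the time of last adequate tumor assessment done prior to the therapy start date".
- Protocol 10.4.3: "The censoring date will be the date of last adequate tumor assessment before the cut-off date".

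Protocol 14.3.26 defines the date: "Date of last adequate tumor assessment is the date the last tumor assessment with overall lesion response of CR, PR or SD", made before the event or censoring reason, with randomization used if there is no post-baseline assessment. Row G of Table 3-3 censors deaths from causes other than the study indication at the last adequate assessment, but not for PFS; time to progression is the endpoint it legibly names.

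The COVID-19 sensitivity analysis of OS in SAP 3.8.2.1 also censors at the time of death.

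**The concern.** Vital status is known up to the day of death, so the death date is the natural censoring date for OS. Progression status is known only up to the last adequate scan. In the primary analysis the death is itself an observed PFS event, so follow-up to that date is justified. Item 4 removes the event and leaves progression as the only outcome that could have occurred, yet keeps the patient in the risk set as progression-free through a period with no adequate scan. The plan does not make that assumption for other censored patients with a usable scan, and gives no reason for making it here.

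What is at stake is whether the output can be interpreted. A reader of this table should be able to attribute any difference from the primary result to the COVID-19 deaths alone, under a censoring convention that matches the rest of the report.

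**Working it through.** **1. Longest unscanned gap before a death that still counts as a PFS event.** SAP 2.4.5 sets D2 as the next two scheduled intervals plus twice the one-week window:

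- LATA within 60 weeks of randomization: 8 + 8 + 2 = 18 weeks
- LATA after 60 and up to 68 weeks: 8 + 12 + 2 = 22 weeks
- LATA after 68 weeks: 12 + 12 + 2 = 26 weeks

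All three match the SAP.

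**2. The same COVID-19 death under each rule.** Let L be the time of LATA and g the gap from LATA to death, with no documented progression before death.

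| Gap | Primary analysis | Item 4 as written | Censoring at LATA |
|---|---|---|---|
| g ≤ D2 | event at L + g | censored at L + g | censored at L |
| g > D2 | censored at L (C2(1)) | censored at L + g if read literally; at L if only deaths counted as PFS events are meant | censored at L |

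In the first row item 4 changes only the status, and the g weeks that remain are unassessed. In the second row the literal reading also lengthens follow-up beyond the primary analysis, with no upper limit on g. The number of events is the same whether COVID-19 deaths are censored at L or at L + g.

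**3. Which gap is relevant.** Enrollment closed on 21 July 2017, so on 28 May 2020 every patient was at least 34 months from randomization. Scans are 12-weekly from month 18 and only as clinically indicated after month 36 (protocol 7.2.1.1). Anyone still at risk for PFS therefore falls under the 26-week threshold if their scans were current. Few would be: under the design medians of 7.0 and 11.67 months and exponential times, the event-free proportions at 34 months are 2^(−34/7.0) ≈ 3% and 2^(−34/11.67) ≈ 13%.

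**4. Size of the effect (illustration).** The documents give no number of COVID-19 deaths. Assumptions: 170 patients per arm, the design medians, administrative censoring uniform over 34 to 58 months, and COVID-19 deaths drawn from patients with observed time beyond 20 months. Each has a 26-week gap; there were 300 runs per scenario. The HR is the exponential of the mean log-HR.

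| COVID-19 deaths (control, alpelisib) | HR, censored at LATA | HR, censored at death | Mean change in log-HR | Largest absolute change in a run |
|---|---|---|---|---|
| 0, 1 | 0.6026 | 0.6018 | −0.0012 | 0.0036 |
| 0, 3 | 0.5968 | 0.5946 | −0.0037 | 0.0094 |
| 0, 5 | 0.5952 | 0.5918 | −0.0058 | 0.0123 |
| 2, 3 | 0.6074 | 0.6108 | +0.0057 | 0.0164 |

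The average HR moves by 0.0008 to 0.0034. The direction depends on which arm the deaths fall in.

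**The case against.** The strongest defense is that, for a death within D2, the primary analysis already follows the patient to the death date. Item 4 then changes the status and nothing else, which is the smallest change that isolates COVID-19 deaths. Censoring at LATA would change both status and time. This is correct, and it is a real cost of the fix. A reader might infer that item 4 always mixes two changes, or adds follow-up relative to the primary analysis; for deaths within D2 it does neither. What remains is that follow-up to the death date was justified by the death being the event, and item 4 removes that justification.

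It can also be said that a death after two or more missed scans is not a PFS event under C2(1), so a rule about death events leaves it alone. That reading is available, and the OS version does speak of deaths rather than death events. Item 4 does not say which is meant. Gaps longer than 26 weeks therefore arise only on the literal reading and cannot be claimed as a general consequence.

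Finally, a reader might infer that item 4 is the only departure from last-scan censoring anywhere in the plan. It is not. For patients with no baseline scan, "these patients are censored in the PFS analysis at the date of randomization" under A(1). Option F(3), the start of new therapy, is listed but not selected. Protocol 10.4.4 speaks loosely of the onset of new therapy, which the SAP resolves to the last scan. The comparison holds for the rules in use for patients with a usable scan.

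**Conclusion.** The inconsistency is real but minor. Item 4 credits up to 18, 22 or 26 weeks of unassessed time per affected patient as progression-free. On the literal reading it also overrides C2(1) for deaths after two or more missed scans. Row G shows that the same guideline, faced with a death it does not count, goes back to the last adequate assessment, although that row does not govern PFS.

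The documents do not support reading this as a threat to the PFS conclusion. Item 4 is a sensitivity analysis, run only if primary PFS is significant and a COVID-19 death occurs. It enters no boundary, and the primary test, alpha and power are untouched. The estimated HR shift, below 0.004 on average, rests on the assumed one to five deaths, 26-week gaps and exponential times. Longer gaps on the literal reading were not simulated. The case for changing item 4 is consistency and clear wording.

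**What to change.** In item 4, state that COVID-19 deaths without earlier documented progression are censored at the last adequate tumor assessment before death. List the remaining options as in the primary analysis: A(1), B(1), C1(1), C2(1), D(1), E(1) and F(1). Naming C2(1) also settles how deaths after two or more missed scans are handled. Keep the date of death in the OS version.

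The cost is one phrase in the SAP and a one-line programming change. The downside is that, for deaths within D2, both time and status will then differ from the primary analysis; a table footnote should say so. If the team prefers the death date for that reason, item 4 should give the reason and confirm that deaths already censored under C2(1) stay at the last adequate assessment.
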